### 6.5.1 PERMITTED THERAPIES

Use of daily washes are required for all subjects participating in the study. Permitted washes are limited to chlorhexidine gluconate, triclosan, benzoyl peroxide, dilute bleach in bathwater, or soap and water.

Starting on Day 1 and if a subject's pain worsens, subjects that require analgesia will be allowed to use ibuprofen (at a dose of up to 800 mg po every 6 hours, not to exceed 3.2 grams/24 hours) and/or acetaminophen as per local labeling. Pain uncontrolled with ibuprofen/acetaminophen may be controlled with tramadol (at a dose of up to 100 mg po every 4 hours, not to exceed 400 mg/24 hours) after Investigator discussion with the Medical Monitor). Of note, dose adjustments of ibuprofen, acetaminophen, or tramadol, and use of these analgesics PRN up to the maximum permitted dose and frequency, are allowed during the study. From screening through Week 32, subjects will not be permitted to use any analgesics related to HS pain within 24 hours of a scheduled study visit.

Oral contraceptives should be continued if stable for the last 12 weeks before Day 1 and if stable in dose and dosing regimen and type (brand) and if the subject plans to continue throughout the study period.

Currently authorized nonlive and nonlive-attenuated vaccines, including those for COVID-19 (eg, RNA-based vaccines, protein-based vaccines, and nonreplicating viral vector-based vaccines), are allowed during the study. If it is unclear if a vaccine is permitted, the Medical Monitor should be consulted prior to subjects' receiving a vaccine. Of note, vaccines, including those for COVID-19, should be captured as a concomitant medication and any related symptoms documented as AEs.

All permitted medications should be recorded as concomitant medications.

The Medical Monitor should be notified if a subject receives antibiotics for more than 10 days for adverse events.

### 6.5.2 PROHIBITED MEDICATIONS OR PROCEDURES

Prohibited medications/therapy are listed below in [Table 4](#). The use of a prohibited medication/therapy (unless conditions for use of rescue medications have been met, see [Section 6.6](#)) is a protocol violation and must be recorded in the eCRF. Subjects who receive prohibited rescue treatment will be discontinued from the study and should return for a final ET visit 12 weeks after their last dose. Study procedures at the ET visit should be completed according to the SoA in [Section 1.3](#). In the case of ongoing AEs/SAEs, the subject should be followed up until it has resolved to a stable outcome or subject is lost to follow-up. The date and time of rescue medication administration, as well as the name and dosage regimen of the rescue medication, must be recorded into the eCRF/study database by study site personnel.

All treatments likely to have efficacy in HS need to be discontinued prior to treatment initiation (prior to Day 1) according to [Table 4](#). All medications listed below are also restricted during the study period. If treatment with any of these prohibited treatments is essential, then the subject must notify the study team.

Rescue therapy should be captured in the source documentation and on the appropriate eCRF.

**Table 4: List of Prohibited Medications and Procedures**

Prohibited Medication/Procedure	Washout Period
Prescription topical therapies for the treatment of HS, and over-the-counter topical antiseptic washes, creams, soaps, ointments, gels, and liquids containing antibacterial agents to treat HS (unless clearly specified as permitted in Section 6.5.1 )	2 weeks of Day 1
Oral analgesics (including opioids) for HS-related pain, unless specified as permitted in Section 6.5.1	2 weeks of Day 1
Oral analgesics (including opioids) for non-HS-related pain, unless specified as permitted in Section 6.5.1	2 weeks of Day 1 (except stable use of ibuprofen and acetaminophen as indicated in Exclusion Criterion 17)
Systemic antibiotic treatment for HS. Note: Systemic antibiotic use (including oral or IV) is allowed for treatment of acute bacterial, fungal, or viral infections.	4 weeks of Day 1
Systemic non-biologic therapies with potential therapeutic impact for HS, including MTX, cyclosporine, retinoids, and fumaric acid esters, and oral or injectable corticosteroids (unless clearly specified as permitted; see Section 6.5.1 ).	4 weeks of Day 1
Surgical, laser, or IPL intervention in area with HS lesion except as outlined in Section 6.5.1	4 weeks of Day 1
Phototherapy (PUVA and/or UVB)	4 weeks of Day 1
Nonbiologic investigational drugs	4 weeks or 5 half-lives (whichever is longer) prior to Day 1
Biologics that have a potential to impact HS (eg, adalimumab).	12 weeks or 5 half-lives prior to Day 1, whichever is longer
Live or live-attenuated vaccines. Note: Currently authorized nonlive and nonlive-attenuated vaccines for COVID-19 (eg, RNA-based vaccines, protein-based vaccines, nonreplicating viral vector-based vaccines) are allowed during the study.	12 weeks of Day 1
Drospirenone, chlormadinone acetate, or cyproterone acetate, unless part of a stable contraceptive regimen as described in Section 6.5.1	12 weeks prior to Day 1

## 6.6 RESCUE TREATMENT

In the event that an intolerable painful lesion occurs that requires an immediate intervention, at Week 8 or later, physicians will have the option to perform protocol-allowed interventions. Only

two types of interventions are allowed: injection with intralesional triamcinolone acetonide suspension (at a concentration of up to 5 mg/mL, up to 1 cc) and incision and drainage. If incision and drainage is performed, the required over-the-counter antiseptic wash should continue to be used. New systemic and topical therapies following incision and drainage (including antibiotics) are prohibited. Concomitant use of wound care dressings is allowed; however, options are limited to alginates, hydrocolloids, and hydrogels. If a subject requires more than 2 lesion interventions during each of the double-blind phases of the study, they must be discontinued from the study.

All study visit evaluations must occur before any interventions are performed. Any lesion that undergoes an intervention will be documented in the source. The study site will be required to count any lesion that undergoes an intervention as permanently present from the date of the intervention and must account for it in the source and on the appropriate eCRF. All interventions (including local anesthetics) should be recorded in the eCRF for tracking purposes.

## 6.7 DOSE MODIFICATION

No dose modification is allowed in this study. Study treatment can be interrupted temporarily or permanently if deemed necessary as per the Investigator's discretion.

## 6.8 TREATMENT AFTER THE END OF THE STUDY

All subjects will return to the study site for the EOS (Day 281/Week 40) or ET visit for final safety and EOS assessments. After this visit, subjects should be treated according to the clinical judgment of the subject's physician. Care after EOS/ET will not be provided by AnaptysBio, Inc. Any SAE or pregnancy occurring through the EOS visit should be reported to the pharmacovigilance unit ([Section 8.2.1](#)) and followed up until an outcome is determined.

## 7 STUDY TREATMENT DISCONTINUATION AND SUBJECT DISCONTINUATION/WITHDRAWAL

### 7.1 DISCONTINUATION OF STUDY TREATMENT

The subject's eligibility criteria will be checked prior to administration of the study treatment on Day 1. If a clinically significant finding or AE/SAE is identified after enrollment, the Investigator or qualified designee will determine if the subject can receive the study treatment and continue in the study and if any change in subject management is needed.

Discontinuation from study treatment does not mean discontinuation from the study, and remaining study procedures should be completed as indicated by the study protocol. In case of early withdrawal from the study treatment and study, the subject will be required to attend the ET visit.

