## 4 STUDY DESIGN

### 4.1 OVERALL DESIGN

This is a Phase 2, multicenter, randomized, double-blind, placebo-controlled study to evaluate the efficacy and safety of imsidolimab in adult subjects with HS. This study also will characterize the PK profile of imsidolimab and explore the immune response to imsidolimab in subjects with HS.

To be eligible for this study, subjects must have a clinically confirmed diagnosis of HS with a disease duration of at least 6 months before Day 1. In addition, subjects will have the following characteristics at screening and Day 1: 1) HS lesions present in at least 2 distinct anatomical areas, 1 of which must be Hurley Stage II (ie, single or multiple, widely separated, recurrent abscesses with tract formation and cicatrization) or Hurley Stage III (ie, diffuse or near-diffuse involvement, or multiple interconnected tracts and abscesses across the entire area); 2) total AN count of  $\geq 5$ ; 3)  $\leq 20$  draining fistulas.

The maximum study duration per subject is approximately 44 weeks, which includes a screening period of up to 30 days, followed by a 16-week placebo-controlled period, a 16-week treatment extension period, and an 8-week follow up period. The placebo-controlled period ends at Day 113 (Week 16) and the treatment extension period starts when study treatment is administered at the Week 16 visit. Of note, during the extension period all subjects will receive imsidolimab but their treatment will remain blinded (see [Figure 1](#)).

During the placebo-controlled period, eligible subjects will be randomized (1:1:1) to receive either imsidolimab (at 1 of 2 different regimens) or placebo, SC administered on 4 occasions: Day 1, Day 29 (Week 4), Day 57 (Week 8), and Day 85 (Week 12). Randomization will be stratified based on Hurley Stage at baseline (Stage II or III).

The treatment arms during the placebo-controlled period will be as follows:

1. Imsidolimab 400 mg on Day 1, followed by 200 mg on Days 29, 57, and 85
2. Imsidolimab 200 mg on Day 1, followed by 100 mg on Days 29, 57, and 85
3. Placebo on Days 1, 29, 57, and 85

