Once the subject has provided an informed consent and meets all inclusion and no exclusion criteria, the study site will request the treatment assignment on Day 1 and Day 113 using a central Interactive Web Response System (IWRS). The process for breaking the blind will be handled through the IWRS. Unblinding is undertaken by a predetermined process to ensure that participating subject and study team are not unblinded unnecessarily and the study results are not compromised. Unblinding of treatment assignment during the study should occur only if it is necessary to know what treatment the subject received during the placebo-controlled period. Unblinding should occur if the Investigator deems identification of the study treatment is necessary for the purpose of providing urgent subject care, and knowledge of the subject’s

treatment assignment (imsidolimab or placebo) will alter subsequent care (emergency unblinding).

In the event that emergency unblinding is necessary, the Investigator must ensure that the unblinding of the treatment code is performed in a discrete manner and the treatment is disclosed only to those persons involved with the direct medical care of the subject. The Investigator must provide the reason for unblinding to the Medical Monitor according to ANB instructions following emergency unblinding. Subjects for whom the blind has been broken will be discontinued from treatment at the time of unblinding. After discontinuation from treatment, subjects should remain in the study for the duration of the safety follow-up period and complete the Day 281 (Week 40) EOS/ET visit 12 weeks after their last dose of study treatment.

AnaptysBio and the contract research organization (CRO) must be notified when a subject and/or Investigator is unblinded during the study. The IWRS will create the blinded and/or unblinded notification when the blind is broken, which can be sent via email as per the user role of IWRS. The unblinding will be captured in the IWRS audit trail. Pertinent information regarding the circumstances of unblinding of a subject's treatment code must be documented in the subject's source documents.

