### 7.2 SUBJECT DISCONTINUATION/WITHDRAWAL FROM THE STUDY

A subject may withdraw from the study at any time at his or her own request or may be withdrawn at any time at the discretion of the Investigator for safety, behavioral, compliance, or administrative reasons.

In case of early withdrawal from the study treatment, the subject will be required to attend an ET visit at the time the decision is made to stop study treatment early (see the SoA in [Section 1.3](#)). After completion of the ET visit, the subject should then return for a final follow-up EOS/ET visit approximately 12 weeks after receiving their last dose of study treatment. Subjects must be withdrawn from the study under the following circumstances, any SAE or AE which, in the opinion of the Investigator, warrant study discontinuation for safety reasons, or pregnancy occurring through the EOS, which should be followed up until outcome.

The following events are considered sufficient reasons for discontinuing a subject from the study treatment and/or the study:

- Pregnancy (refer to [Appendix 1](#) and [Section 8.2.1.8](#))
- Significant deviation/lack of compliance with protocol
- Any significant AE, laboratory abnormality, or other medical condition or situation occurs such that continued participation in the study would not be in the best interest of the subject in the opinion of the Investigator
- Disease progression which requires discontinuation of the study treatment
- Withdrawal of consent
- Lost to follow-up
- Use of any prohibited medication or treatment that in the opinion of the Investigator necessitates the subject being withdrawn (refer to [Section 6.5.2](#))
- Termination of the subject's participation by the Investigator or AnaptysBio

The reason for subject discontinuation or withdrawal from the study will be recorded on the eCRF.

If a subject withdraws from the study, he or she may request destruction of any samples taken and not tested, and the Investigator must document this in the study site study records.

See SoA ([Section 1.3](#)) for data to be collected at the time of study discontinuation and follow-up and for any further evaluations that need to be completed.

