### 6.2.1 Study Day and Visit Window Definitions

Efficacy data obtained from unscheduled visits [not including the End of Study visit] will be allocated to the scheduled visit corresponding to the visit window they fall in as specified in **Table 2**. Efficacy data will be analyzed based on the nominal visits and nominal time points. If there is no pre-dose assessment for the window, then the closest post-dose assessment may be used instead. Only if the data from the nominal visit or time point is missing or falls outside the visit window will data from unscheduled visits for the same nominal visit or time point be used in analysis. Unscheduled visits will only be considered for use at an analysis time point if they fall within the respective window. If more than one unscheduled visit exists in a given window, the measurement closest to, but not after, the nominal day will be used in analysis. Efficacy data from scheduled and unscheduled visits will be listed.

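### Protocol 7.1 and 7.2 give conflicting visit rules for a subject who stops treatment but stays in the study, and the SAP does not say how an early ET/EOS visit maps to Week 16

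*Protocol*

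**What the plan says.** Protocol 7.1: "Discontinuation from study treatment does not mean discontinuation from the study, and remaining study procedures should be completed as indicated by the study protocol". The next sentence limits the ET visit: "In case of early withdrawal from the study treatment and study, the subject will be required to attend the ET visit".

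Protocol 7.2 is headed as discontinuation from the study, but its operative sentence is triggered by withdrawal from study treatment: "the subject will be required to attend an ET visit at the time the decision is made to stop study treatment early". After that, "the subject should then return for a final follow-up EOS/ET visit approximately 12 weeks after receiving their last dose of study treatment". It names no visits in between.

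Protocol 6.3, on emergency unblinding, takes subjects off treatment, keeps them for safety follow-up and has them "complete the Day 281 (Week 40) EOS/ET visit 12 weeks after their last dose of study treatment".

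The Schedule of Activities gives EOS and ET a single column, labelled D281 (W40) with a window of ±5 days. The ET visit carries all EOS procedures, which include the AN count.

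SAP 6.2.1 analyses efficacy by nominal visit and allocates other data by window: "Efficacy data obtained from unscheduled visits [not including the End of Study visit] will be allocated to the scheduled visit". SAP Table 2 sets Week 16 at Days 109 to 136 and Week 40 at Days 276 to 286. SAP 6.6.1 applies the 6.2.1 rules to scheduled safety assessments. SAP 7.9 has a separate rule for laboratory, ECG and vital-sign summaries that uses unscheduled data within the window when the scheduled value is missing, with no End of Study exception.

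**The concern.** One event, stopping treatment without leaving the study, has two visit patterns. A site reading 7.1 would keep the subject on the full schedule, including Day 113. A site reading 7.2 would see the subject twice more and close the case. Whether a Week 16 AN count exists, and how often safety is assessed, would then depend on the site's reading.

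That matters for the primary endpoint because stopping may be linked to adverse events or lack of effect, and SAP 7.1.2 says the MMRM relies on missing at random. Some missing counts would come from procedure rather than from the subject's absence. A count that is taken close to Day 113, but recorded as an ET or EOS visit, might still not be used.

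**Working it through.** **The plan's own figure.** Inputs from Protocol 9.2: difference 4.9, SD 8.2, two-sided alpha 0.10, 36 evaluable per arm after 10% discontinuation from 40. The noncentrality is 4.9 / (8.2 × √(2/36)) = 2.54 on 70 degrees of freedom, giving power of 80.7%. The stated 80% is reproduced. With all 40 per arm evaluable and the effect unchanged, power is 84.2%. At most about 3.5 points of power are at stake.

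**Visit dates under 7.2.** Inputs: dosing on Days 1, 29, 57 and 85 (Protocol 4.1), final visit = last dose + 84 days (7.2), and the SAP Table 2 windows. The decision to stop is assumed to come no later than the next scheduled dosing day.

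| Last dose | Final visit | Its SAP window | ET visit falls in | Visit in Days 109–136? |
|---|---|---|---|---|
| Day 1 | 1 + 84 = 85 | Week 12 | Days 2–29 | No |
| Day 29 | 29 + 84 = 113 | Week 16 | Days 30–57 | Yes, the final visit |
| Day 57 | 57 + 84 = 141 | Week 20 | Days 58–85 | No, except at the edge: 141 − 5 = 136 |
| Day 85 | 85 + 84 = 169 | Week 24 | Days 86–113 | Only if the decision comes on Days 109–113 |

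The same ±5 days could move the Day 29 subject's final visit to Day 108, just outside the window. Subjects who stop after the Day 113 dose already have their Week 16 count.

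**Share without a Week 16 visit.** No document gives stopping times. Assume equal weight on the four last-dose days and visits on the target day.
- Decisions made at the next scheduled visit: (0 + 1 + 0 + 1)/4 = 50% have a visit in the window, so 50% do not.
- Decisions spread evenly over the 28 days between doses: the Day 85 group contributes 5/28 = 0.179. Then (0 + 1 + 0 + 0.179)/4 = 29.5% have one, so about 70% do not.

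The planned 10% is 12 of 120 subjects, about 4 per arm. If all 12 stopped treatment but stayed in the study (the documents do not say so), 12 × 0.50 = 6 to 12 × 0.705 ≈ 8 would have no visit in the window under 7.2.

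**Number of visits after the last dose, full schedule against 7.2.** Day 1: 10 against 2. Day 29: 9 against 2. Day 57: 8 against 2. Day 85: 7 against 2. The 84-day span is the same as for completers (197 + 84 = 281), who have three visits in it: Days 225, 253 and 281.

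**Mapping.** An EOS/ET-labelled visit on Day 113 has a Week 40 label but lies outside the Week 40 window, and 6.2.1 excepts the End of Study visit from allocation by window. Nothing in the SAP says whether an early ET visit counts as that End of Study visit or as an unscheduled one.

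**Section 6.3.** The visit 12 weeks after the last dose is Day 281 only when the last dose is Day 197. For any earlier last dose the two descriptions in that sentence name different days.

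**The case against.** The strongest reply is that the sections can be read together. Section 7.2 has a study-withdrawal heading, and 7.1 refers remaining procedures to the protocol, which could mean 7.2. This does not settle the matter: the 7.2 sentence speaks of study treatment, and the next sentence of 7.1 reserves the ET visit for those who leave both.

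A second reply is that the analysis already copes. The sample size allows for 10% loss, subjects missing Week 16 stay in the MMRM (SAP 7.5.1), and multiple imputation and a tipping-point analysis are planned (SAP 7.5.4). That stands, and power is not the issue. But these methods handle missing counts without recovering them. It is also fair that using off-treatment counts is an estimand choice: the documents name a hypothetical strategy with rescue as the example and name none for stopping treatment.

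Four stronger readings are tempting and are not supported.
- *Most subjects who stop have no Week 16 visit.* This rests on assumed stopping times. A Day 29 last dose, a decision on Days 109 to 113, and any stop in the extension all leave a Week 16 visit.
- *Safety follow-up is cut short relative to exposure.* The 84 days after the last dose are kept. AEs are still reviewed continuously, and clinically significant laboratory values are repeated until resolved or stable (Protocol 8.2.7). What falls is the number of visits.
- *Safety values from the ET visit drop out of the by-visit tables.* SAP 7.9 has its own rule without the End of Study exception, and all data are listed. The mapping is unclear; exclusion is not shown.
- *Section 6.5.2 is a third pattern.* It says "Subjects who receive prohibited rescue treatment will be discontinued from the study and should return for a final ET visit 12 weeks" after the last dose. That concerns subjects discontinued from the study, a different trigger, and fits the final visit in 7.2.

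**Conclusion.** The conflict between 7.1 and 7.2 is real for a subject who stops treatment and has not left the study, and the text does not resolve it. Under 7.2, subjects last dosed on Day 1 have no visit in the Week 16 window. Nor do those last dosed on Day 57 (apart from Day 136) or those who stop after the Day 85 dose and before Day 109. The share of pre-Week-16 stoppers affected is unknown; 50% to 70% holds only with equally likely last-dose days and decisions no later than the next dosing day. It would approach 100% if EOS/ET-labelled visits are never mapped to Week 16, which the SAP leaves open. The consequence is site-dependent follow-up and avoidable missing primary-endpoint data in a small group, not a loss of planned power. The arithmetic is certain; the size in practice is not.

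**What to change.** **Protocol.** Reconcile 7.1 and 7.2 so that stopping treatment and leaving the study each have one visit pattern. Align 6.3, so that its final visit is not described both as Day 281 and as 12 weeks after the last dose. State explicitly whether the scheduled Day 113 AN count is collected from treatment-discontinued subjects still in the study, as 7.1 already implies. This concerns visits and data collection only; no rule for stopping treatment is proposed.

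**SAP 6.2.1 and 6.6.1.** State that ET- or EOS-labelled assessments taken before the Week 40 window are allocated to analysis windows by actual study day, and make 6.6.1 and 7.9 agree.

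**Cost.** A protocol amendment with IRB/EC approval and a short SAP revision. If the 7.1 pattern is kept, some subjects off treatment attend more visits than under 7.2. If the 7.2 pattern is kept and a Day 113 count is wanted, that is an added visit for some subjects: after a Day 1 last dose, 7.2 ends on Day 85.
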